## 1.6 Sample Size and Power Considerations

The protocol (Section 9.1) includes the following statements about sample size and power considerations:

The primary objective is to evaluate the effect of azeliragon plus SoC on cognition and functional outcome by comparing azeliragon plus SoC with placebo plus SoC. The co-primary endpoints are change from Baseline on the ADAS-cog total score at Month 18 and change from Baseline on the CDR-sb total score at Month 18. The study includes AD patients with mild disease as defined by having a baseline MMSE of 21 through 26.

This trial includes two independent sub-studies, each of which is supported by randomization independently, because randomization by investigative site is used. Each sub-study is powered using  $\alpha = 0.05$ .

Approximately 160 subjects (80 per treatment group) will be enrolled and participate in the FDG-PET sub-study. The sample size for this sub-study was selected empirically.

Sample size calculations are done to power each study (A-study and B-study) separately. It is anticipated that each A-study and B-study will randomize approximately  $N=400$ .

Assuming a standard deviation of the change from Baseline to Month 18 in ADAS-cog of 9 (based on Study TTP488-203), using  $\alpha = 0.05$ , a total sample size of 282 patients in balanced allocation (141 patients per group) provides at least 90% power to detect a difference between treatment groups of 3.5 (based on data from mild AD patients in Study TTP488-203) using a 2-sided, 2-sample t-test. Assuming a dropout rate of 20% or less, randomization of 354 patients provides adequate statistical power for this study to demonstrate superiority of azeliragon plus SoC over placebo plus SoC based on the ADAS-cog.

Assuming a standard deviation of the change from Baseline to Month 18 in CDR-sb of 2.4, using  $\alpha = 0.05$ , a total sample size of 304 patients in balanced allocation (152 patients per group) provides at least 90% power to detect a difference between treatment groups of 0.9 (based on data from mild AD patients in Study TTP488-203) using a 2-sided, 2-sample t-test. Assuming a dropout rate of 20% or less, randomization of 380 patients provides adequate statistical power for this study to demonstrate superiority of azeliragon plus SoC over placebo plus SoC based on CDR-sb.

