- The imputed datasets generated with the approach described above do contain only non-missing values and are used as input in the model for the supportive analysis of the primary endpoint. MMRM models similar to what are described above will thus be run on each of the generated imputed datasets and the difference between the treatment groups at Month 18 will be estimated. The MMRM model will be similar to the primary analysis. Finally, the MIANALYZE procedure in SAS will be applied to combine the results from these several datasets to derive an overall estimate of the treatment difference at Month 18. In addition to the estimates, corresponding 95% confidence intervals and p-values will be calculated.

Another MI analysis will be performed with the assumption that the data in the active treatment group are missing not at random (MNAR). A tipping point-based assumption will be used, i.e. the trajectories of the patients in the active treatment group after withdrawal are assumed to be worse by an amount of delta. After the MI using the MAR assumption, as defined above has been done, the amount of delta will be added to each imputed value in the active treatment group. Successively harsher deltas will be imposed on the imputed values in the active group, starting with an ADAS-cog increment (worsening) of 0.25 points or a CDR-sb increment

(worsening) of 0.1 points. The delta is further increased in the steps of 0.25 points (e.g., 0.50, 0.75) for ADAS-cog or in the steps of 0.1 points (e.g., 0.2, 0.3) for CDR-sb until the statistical significance is lost, i.e., until the p-value becomes more than 0.049. For the placebo group, the MI using MAR assumption will be used.

Further MI analysis assuming MNAR will be done using the Copy Reference approach. Placebo-group based assumption will be used, i.e. the trajectories of the patients are assumed to follow the placebo group after the discontinuation. Methods similar to those described above will be used to generate monotone missing data. After this, the missing data will be imputed sequentially for each visit (e.g., Month 3, Month 6). Only the data from the placebo group will be used for the imputation.

For the ANCOVA models, data from baseline and Month 18 will be used. Analysis will include treatment, baseline stratum as fixed factors and Baseline as covariate. For the LOCF analysis, the last available measurement will be used to impute the Month 18 data in case of missing data.

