Rank analogues (e.g., Wilcoxon analysis, rank ANCOVA, and van Elteren analysis when strata are a part of the approach) will be used for additional supportive analyses. An observed-cases analysis will be done by visit.

An essential component of the thorough analysis includes an assessment of the impact of missing data on study conclusions. As a part of assessing this impact, sensitivity analysis will include an endpoint analysis (reduction to last-observation-carried-forward, justified in this study based on the monotonic progression of the natural course of AD and assuming no more dropouts in the group treated with azeliragon plus SoC than in the group treated with placebo plus SoC), a completers analysis (observed cases at Month 18), and observed cases by assessment time.

Interaction terms will be examined in the supportive analyses. The primary model will not include interaction terms with covariates. In the event of a significant interaction term, the impact on analysis conclusion will be examined. A key sensitivity analysis will use the ITT methodology and a main-effects model for ANCOVA adjusting for baseline ADAS-cog (CDR-sb) using last-observation-carried-forward (LOCF) methods for missing data, justified based on known profiles of ADAS-cog (CDR-sb) in AD patients, which is conservative under the assumption that there are not more dropouts in the active-treated group than the placebo group. Rank ANCOVA will be done as a supportive analysis.

Additional unplanned sensitivity analyses may be performed.

Descriptive summaries will be produced of the observed values and change from Baseline in co-primary variables by treatment group at each individual time point and at endpoint (final on-treatment assessment for each subject).

For statistical analyses, 95% confidence intervals will be produced for the least-squares means (LSM) in each treatment group, as well as the LSM differences as compared to placebo plus SoC. For MMRM and ANCOVA, two-sided p-values will be displayed for the comparison against placebo plus SoC.

Because there are limited numbers of subjects per center, there will be inadequate power to explore the impact of the center effect on study conclusion. Descriptive statistics by center will be presented.

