### 6.2 Missing Data

In general, missing clinical data will not be imputed, except where explicitly defined. In the event of study withdrawal, a subject's final assessment will be used as the endpoint value, if applicable. For Trail Making Test A & B, if the assessment was not done due to cognitive reasons, the max score would be imputed. Note that the reason for "not-done" assessment is captured in the eCRF, and the specify field provides reason why. If the reason relates to cognitive reasons, the maximum time for Trails A (150 seconds) or for Trails B (300 seconds) is used.

Data are considered to be "on-treatment" if the assessment or collection follows the first administration of study medication and if the assessment occurs within 45 days following the final administration of study medication, justified based on the long half-life of this drug.

Dates with missing fields will not have days imputed.

In accordance with the recommendations of the report from the National Academy of Science (NAS) panel "*The Prevention and Treatment of Missing Data in Clinical Trials*," (National Research Council, 2010), sensitivity analyses will be done to ensure that study conclusions are robust against missing data. Last observation carried forward (LOCF) and baseline observation carried forward (BOCF) methods may be used as appropriate in sensitivity analysis. Missing data types will be examined, and statistical methodologies for appropriate sensitivity analyses will be finalized during blind data review as patterns emerge as the study progresses. Primary methodologies following the ITT principle are not subject to change.

The three types of missing data ([Rubin, 1976](#)) are considered to examine robustness of analysis conclusions against missingness and type of missingness:

- MCAR (missing completely at random) assumes the event of missingness is independent both of observable values and of unobservable values, and the missingness is entirely at random.
- MAR (missing at random) assumes that the missingness can be fully accommodated by accounting for variables where data are available.

- MNAR (missing not at random) the missingness may be related to the reason the data are missing.

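### The SAP calls its LOCF sensitivity analysis conservative if active has no more dropouts than placebo, but a condition on dropout numbers alone does not ensure this, because exit timing also matters.

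*SAP*

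**What the plan says.** The primary analysis in SAP 5.2.1 is an MMRM on change from baseline at Month 18, run separately in A-study and B-study. Several missing-data analyses surround it. One sentence begins "A key sensitivity analysis will use the ITT methodology and a main-effects model for ANCOVA adjusting for baseline ADAS-cog (CDR-sb" and goes on to specify LOCF for missing values, a method described as one "which is conservative under the assumption that there are not more dropouts in the active-treated group than the placebo group". The mechanics are given earlier in the section: "For the LOCF analysis, the last available measurement will be used to impute the Month 18 data in case of missing data". The related LOCF endpoint analysis is "justified in this study based on the monotonic progression of the natural course of AD", again assuming no excess of dropouts on active.

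Protocol 9.5.2 carries the same reasoning but calls the LOCF ANCOVA a key supportive analysis. Neither document attaches a condition on when patients leave.

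SAP 5.2.1 also plans multiple imputation under missing at random, a tipping-point analysis that worsens imputed values on active step by step, and a reference-based analysis: "Further MI analysis assuming MNAR will be done using the Copy Reference approach". None of these is labelled key.

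**The concern.** If patients worsen steadily, LOCF stops the clock at the exit visit, and the earlier the exit, the milder the score carried to Month 18. The direction of the LOCF error therefore depends on when patients leave in each arm as well as on how many leave. Two arms can have identical dropout numbers, satisfy the SAP's condition, and still give an LOCF comparison that leans toward active.

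What is at stake is how a positive result would be read. Protocol 1.1.3 already cites an LOCF p-value among the analyses confirming the robustness of the Phase 2 finding. If active patients tended to leave early and placebo patients late, an LOCF result described in advance as conservative would lend support that it had not earned.

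**Working it through.** **The plan's own figures.** The LOCF sentence gives no number. The sample-size inputs used below (SAP 1.6) do reproduce. For ADAS-cog, SD 9, difference 3.5 and 141 per group give power 0.902 (exact two-sided t-test, alpha 0.05), and 282/0.8 = 352.5, or 354 rounded up to an even number. For CDR-sb, SD 2.4, difference 0.9 and 152 per group give power 0.903, and 304/0.8 = 380.

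**Inputs from the documents.** Dropout share d = 0.20 (SAP 1.6 plans for 20% or less); planned ADAS-cog effect δ = 3.5; about 400 randomized per sub-study, so 200 per arm; test level 0.049 (SAP 5.2); scheduled post-baseline ADAS-cog visits from Month 3 (SAP 4.1.5.1).

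**Assumptions not in the documents.** The placebo decline D over 18 months (5 to 9 ADAS-cog points, 1.5 to 3 CDR-sb points); linear decline; dropouts following their arm's mean course up to exit; the mean exit months; and SD 9 or 2.4 applied to the LOCF change.

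**Formula.** Let tA and tP be mean exit time on active and placebo as fractions of 18 months. LOCF omits the decline after exit, so with equal dropout share

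bias toward active = d × [(D − δ)(1 − tA) − D(1 − tP)].

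**No drug effect (δ = 0).** This reduces to d × D × (tP − tA), which is zero for equal timing and positive for any earlier active exit. The type I error below is that of the LOCF test alone, from a normal shift of bias/SE, with SE = 9 × √(2/200) = 0.90.

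| Mean exit, active vs placebo | D | Bias toward active | Type I error |
|---|---|---|---|
| Month 6 vs 9 | 5 | 0.20 × 5 × 3/18 = 0.17 | 0.053 |
| Month 6 vs 9 | 9 | 0.20 × 9 × 3/18 = 0.30 | 0.062 |
| Month 3 vs 12 | 5 | 0.20 × 5 × 9/18 = 0.50 | 0.085 |
| Month 3 vs 12 | 9 | 0.20 × 9 × 9/18 = 0.90 | 0.168 |

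Against the planned 3.5 points, 0.17 to 0.30 is 5 to 9%, and 0.5 to 0.9 is 14 to 26%. A 6000-run simulation at D = 6 agreed with the formula: Month 6 vs 12 gave 0.071 (formula 0.072), and Month 3 vs 15 gave 0.142 (formula 0.142).

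For CDR-sb (SE = 2.4 × √(2/200) = 0.24), Month 6 vs 9 gives 0.05 to 0.10 points and type I error 0.054 to 0.069. Month 3 vs 12 gives 0.15 to 0.30 points and 0.094 to 0.237.

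**Fewer dropouts on active.** With 16% on active and 20% on placebo, Month 3 vs 15 and D = 6, the bias is 6 × (0.16 × 15/18 − 0.20 × 3/18) = 0.60 toward active. The SAP's condition is met strictly, and LOCF still leans toward active.

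**True effect of 3.5.** LOCF now also discards part of the benefit, so it overstates the effect only if (1 − tA)/(1 − tP) > D/(D − δ). Bias in points:

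| Mean exit, active vs placebo | D = 5 | D = 7 | D = 9 |
|---|---|---|---|
| Month 6 vs 9 | −0.30 | −0.23 | −0.17 |
| Month 4.5 vs 10.5 | −0.19 | −0.06 | +0.08 |
| Month 3 vs 12 | −0.08 | +0.12 | +0.32 |

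LOCF understates the effect in 6 of the 9 cells, including every cell with modestly earlier active exit.

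**The case against.** The strongest reply is that little depends on LOCF. SAP 5.2.1 declares success only if the primary analysis reaches p below 0.049 on both endpoints in both sub-studies. SAP 6.2 says robustness is managed through multiple imputation, with a delta adjustment toward placebo for the active group. A reader would see LOCF beside the tipping-point and Copy Reference results, and SAP 9 plans a withdrawal listing with study day and reason. Early exit on 5 mg is also hypothetical: the protocol summary calls that dose well tolerated, and protocol 1.1.3 did not find the 20 mg/day group's falls and confusion signal at 5 mg/day. Patients who leave after marked worsening would carry poor scores forward, which works against active. The Month 3 versus 12 case requires nearly all active dropouts to leave around the first scheduled efficacy visit.

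These points limit the size and consequence of the problem. They do not make the sentence true, because the count condition still does not deliver the property claimed for it. A listing also shows individual exits; neither document plans a by-arm summary of exit timing.

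Three stronger readings are tempting and are not supported:

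- *LOCF favours active whenever active patients leave earlier.* This follows only with no drug effect. With the planned effect it fails in most of the cells above.
- *LOCF could by itself manufacture a benefit.* It cannot, because the success rule does not use it.
- *BOCF is worse on this score.* SAP 6.2 says "baseline observation carried forward (BOCF) methods may be used as appropriate in sensitivity analysis". BOCF gives every dropout zero change whatever the exit month, so timing cannot bias it. At equal counts its bias is 0 with no effect, and −0.20 × 3.5 = −0.7 points (against active) with the planned effect.

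**Conclusion.** The concern holds in limited form. Under the SAP's own premise of monotone decline, having no more dropouts on active is not sufficient for LOCF to be conservative. With no drug effect, equal numbers and 20% dropout, the ADAS-cog bias toward active is 0.17 to 0.30 points for a plausible timing gap and 0.5 to 0.9 for an extreme one. When the drug works, LOCF may remain conservative despite modestly earlier active exit.

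The sizes rest on an assumed decline of 5 to 9 points, linearity, and exit months that the documents do not give. The direction with no drug effect needs only monotone mean decline and dropouts who follow their arm's course. The primary MMRM and the success rule are untouched; the risk is false reassurance about robustness from an analysis labelled key. The wording should be changed, but this does not threaten the trial's main inference.

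**What to change.** In SAP 5.2.1:

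1. Delete the statement that LOCF is conservative, or condition it on both the number and the timing of dropout in each arm. Treat the count-only justification of the LOCF endpoint analysis in the same way.
2. Name the planned Copy Reference imputation as the key sensitivity analysis for both co-primaries, with the tipping point second.
3. Keep LOCF as a descriptive or supportive analysis.
4. Add a by-arm summary of time to dropout and reason for dropout, within each sub-study.

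The SAP supersedes the protocol (protocol 9.0), so a note of the change from protocol 9.5.2 in SAP 1.9 should suffice. The cost is SAP wording and one summary table. Both replacement analyses are already planned, and the withdrawal dates and reasons are already to be listed. The change should be made before unblinding.

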Three interim analyses were planned during the study. The first interim analysis was conducted 6 months after approximately 50% of participants had been randomized. This analysis was conducted for the purposes of safety and for informing internal development decisions. The second interim analysis was conducted 12 months after all participants were randomized to assess futility, as well as for safety and to inform internal development decisions. A third interim analysis to inform internal development decisions was to be conducted when all continuing participants completed the Month 18 visit.

The first pre-specified interim safety analysis revealed an increased frequency of AEs (concentration related and reversible upon discontinuation of treatment), in particular falls and confusion, in the 20 mg/day group relative to the 5 mg/day and

placebo groups. This was associated with a higher percentage of participants in the 20 mg/day group declining by ≥ 10 points on the ADAS-cog (relative to Baseline scores) at Months 3 and 6 (concentration related and stabilized/reversible upon discontinuation of treatment). These findings were not noted for the 5 mg/day group or the placebo group. On the recommendation of the Data and Safety Monitoring Board (IDMC), participants randomized to the 20-mg/day dose discontinued study drug, received a safety evaluation, and were asked to consent to continue to be followed for safety clinical and laboratory assessments.

Approximately 12 months after all participants were randomized, the second pre-specified interim analysis compared 5 mg/day and placebo for futility based on results of the completer population (i.e. those with available 18-month ADAS-cog data). Conditional power was computed based on assumed continuation of the observed trend.

While safety data raised no concerns, criterion for futility ($< 10\%$ conditional power to observe a significant difference between 5 mg/day and placebo at 18 months) was met and treatment was discontinued. The third interim analysis was not performed as the study was terminated due to futility. Attempts to replicate the futility analysis, using a data set representative of that which would have been used for the futility analysis (constructed from the final data set) have been unsuccessful with conditional probabilities consistently computed as $> 20\%$.

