9.1 SAMPLE SIZE DETERMINATION

The primary objective is to evaluate the effect of azeliragon plus SoC on cognition and functional outcome by comparing azeliragon plus SoC with placebo plus SoC. The co-primary endpoints are change from Baseline on the ADAS-cog total score at Month 18 and change from Baseline on the CDR-sb total score at Month 18. The study includes AD patients with mild disease as defined by having a baseline MMSE of 21 through 26.

This trial includes two independent sub-studies, each of which is supported by randomization independently, because randomization by investigative site is used. Each sub-study is powered using $\alpha = 0.05$.

Approximately 160 subjects (80 per treatment group) will be enrolled and participate in the FDG-PET sub-study at select sites in the United States and Canada. The sample size for this sub-study was selected empirically.

Sample size calculations are done to power each study (A-study and B-study) separately. It is anticipated that each A-study and B-study will randomize approximately N=400 each.

Assuming a standard deviation of the change from Baseline to Month 18 in ADAS-cog of 9 (based on Study TTP488-203), using $\alpha = 0.05$, a total sample size of 282 patients in balanced allocation (141 patients per group) provides at least 90% power to detect a difference between treatment groups of 3.5 (based on data from mild AD patients in Study TTP488-203) using a 2-sided, 2-sample t-test. Assuming a dropout rate of 20% or less, randomization of 354 patients provides adequate statistical power for this study to demonstrate superiority of azeliragon plus SoC over placebo plus SoC based on the ADAS-cog.

Assuming a standard deviation of the change from Baseline to Month 18 in CDR-sb of 2.4, using $\alpha = 0.05$, a total sample size of 304 patients in balanced allocation (152 patients per group) provides at least 90% power to detect a difference between treatment groups of 0.9 (based on data from mild AD patients in Study TTP488-203) using a 2-sided, 2-sample t-test. Assuming a dropout rate of 20% or less, randomization of 380 patients provides adequate statistical power for this study to demonstrate superiority of azeliragon plus SoC over placebo plus SoC based on CDR-sb.

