9.5.2 Statistical Methodology for Primary Analysis

The primary analysis will use the ITT methodology and a main-effects mixed-models for repeated measures (MMRM) methodology. The MMRM will utilize an unstructured covariance where the number of parameters is $t(t+1)/2$ where t is the dimension of the covariance matrix, using PROC MIXED in SAS. In the unlikely event of lack of convergence, Toeplitz structure will be employed where the number of parameters is t where t is the dimension of the covariance matrix. Time is considered as a class variable. Analysis will include treatment, time and treatment-by-time interaction as fixed effects, Baseline as covariate, baseline stratum as a covariate, and subject as a random effect. Supportive modeling will also include MMRM main-effects model with treatment, time, and subject.

The primary analysis will be done for each sub-study separately and will use $\alpha = 0.049$, which includes an adjustment of 0.001 for interim analyses performed by the Independent Data Monitoring Committee (IDMC), thereby preserving the overall study-wise $\alpha = 0.05$.

The primary analysis will also be done on randomization stratification subgroups defined by (1) baseline ADAS-cog 19 or less and (2) baseline ADAS-cog more than 19.

Multiple imputations (MI) will be used as a supportive analysis with 100 invocations (acknowledging that more invocations are needed with more missing data). Monte Carlo methods are planned.

An essential component of the thorough analysis includes an assessment of the impact of missing data on study conclusions. As a part of assessing this impact, supportive analysis will include an endpoint analysis (reduction to last-observation-carried-forward, justified in this study based on the monotonic progression of the natural course of AD and assuming no more dropouts in the group treated with azeliragon plus SoC than in the group treated with placebo plus SoC), a completers analysis (observed cases at Month 18), and observed cases by assessment time.

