##### 4.1.5.1 Alzheimer's Disease Assessment Scale - Cognitive Subscale 70 point (ADAS-cog):

- Range: The scale range is 0 to 70 with higher scores indicating greater cognitive impairment.
- Brief description: The ADAS-cog is a structured scale (approximately 40 minutes to complete) that evaluates memory, orientation, attention, reasoning, language and constructional praxis (Rosen, 1984). The ADAS-cog scoring range for the version used in this study is from 0 to 70. The ADAS-cog will be conducted at Baseline and at Months 3, 6, 9, 12, 15 and 18 or in the event of early termination. The ADAS-cog should always be administered prior to other cognitive measures.

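### Dropout count alone does not make the key LOCF analysis conservative: equal or fewer azeliragon dropouts can still bias it towards azeliragon if they leave sufficiently earlier.

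*SAP*

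**What the plan says.** The primary analysis of each co-primary endpoint is an MMRM on the full analysis set. Among the sensitivity analyses, SAP 5.2.1 gives LOCF a named role: "A key sensitivity analysis will use the ITT methodology and a main-effects model for ANCOVA adjusting for baseline ADAS-cog (CDR-sb"), with LOCF for missing values. The rule is that "the last available measurement will be used to impute the Month 18 data in case of missing data".

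The same sentence calls this analysis one "which is conservative under the assumption that there are not more dropouts in the active-treated group than the placebo group". The LOCF endpoint analysis in the same section is "justified in this study based on the monotonic progression of the natural course of AD", together with the same condition on numbers of dropouts. Protocol 9.5.2 argues likewise, "assuming no more dropouts in the group treated with azeliragon plus SoC than in the group treated with placebo plus SoC", and repeats the conservatism claim for its LOCF ANCOVA.

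Neither document attaches a condition on when patients leave. SAP 5.2.1 also plans multiple imputation under missing at random, a delta-adjusted tipping-point analysis on the active arm and a Copy Reference imputation. SAP 6.2 rests robustness against missing data on the imputation methods.

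**The concern.** If Alzheimer's disease worsens steadily, as the plan assumes, carrying a value forward deletes all decline between the last visit and Month 18. A patient last seen at Month 3 is spared 15 months of decline; one last seen at Month 15 is spared three. The plan's condition limits how many patients leave each arm but not how much decline is deleted in each. It can therefore be met exactly while LOCF deletes more decline on azeliragon than on placebo.

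What is at stake is how a favourable LOCF result may be cited. Protocol 1.1.3 shows LOCF used in this way: the Phase 2 LOCF result was offered as evidence that the ADAS-cog finding was robust. Here the plan adds in advance the assurance that LOCF leans against the drug, on a test that cannot establish it.

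**Working it through.** **Inputs from the documents.** ADAS-cog SD of change 9 and design difference 3.5; CDR-sb design difference 0.9 (SAP 1.6, Protocol 9.1). Planning assumption on dropout: "Assuming a dropout rate of 20% or less". About 400 patients per sub-study, 1:1, so 200 per arm. Two-sided alpha 0.049 (SAP 5.2). Possible last ADAS-cog visits: "The ADAS-cog will be conducted at Baseline and at Months 3, 6, 9, 12, 15 and 18". CDR is assessed at Months 3, 6, 12 and 18 only.

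**The plan's own figures.** The conservatism claim carries no number. The sample size that supplies the inputs reproduces: 141 per group, SD 9 and difference 3.5 give 90.2% power by t-test at 0.05, and 141/0.8 = 176.25, rounded up to 177 per group, gives the stated 354.

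**Assumptions not in the documents.** Placebo decline D over 18 months: 5 to 9 ADAS-cog points, 1.5 to 3 CDR-sb points. Decline is linear, dropouts follow their arm's mean trajectory, and each arm has a single last-visit month. The exit patterns are illustrative.

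**Formula.** Let f = dropout share × (18 − last month)/18 in each arm, and δ the true benefit. The mean LOCF change is D(1 − fP) on placebo and (D − δ)(1 − fA) on azeliragon. The LOCF benefit is their difference, so

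bias = D(fA − fP) − δ·fA, where positive favours azeliragon.

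The plan's condition restricts only the dropout shares inside fA and fP.

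**ADAS-cog results**, each range for D = 5 to 9:

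| Azeliragon vs placebo (share, last visit) | fA | fP | Bias, δ = 0 | Bias, δ = 3.5 |
|---|---|---|---|---|
| 1. 20% Month 9 vs 20% Month 9 | 0.100 | 0.100 | 0 | −0.35 |
| 2. 20% Month 6 vs 20% Month 12 | 0.133 | 0.067 | +0.33 to +0.60 | −0.13 to +0.13 |
| 3. 15% Month 3 vs 20% Month 15 | 0.125 | 0.033 | +0.46 to +0.82 | +0.02 to +0.39 |
| 4. 10% Month 6 vs 20% Month 9 | 0.067 | 0.100 | −0.17 to −0.30 | −0.40 to −0.53 |

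Example, pattern 3 at D = 9: 9 × (0.125 − 0.0333) = 0.825; subtracting 3.5 × 0.125 = 0.4375 leaves +0.39.

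All four patterns meet the plan's condition. Patterns 2 and 3 favour azeliragon under no effect; pattern 4, also with fewer and earlier azeliragon exits, goes the other way. With a true benefit, LOCF favours the drug only if fA/fP > D/(D − δ). In pattern 2 the ratio is 2.0, and the bias is zero at D = 7, where 7/(7 − 3.5) = 2.0.

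**CDR-sb, pattern 2.** Under no effect, 0.0667 × 1.5 to 3 = +0.10 to +0.20. With a true 0.9, subtract 0.9 × 0.133 = 0.12, giving −0.02 to +0.08.

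**Rejection rate of the LOCF test under no effect.** SE = 9 × √(2/200) = 0.90. By normal approximation at two-sided 0.049, the rate is about 6.5% to 10% in pattern 2, 8% to 15% in pattern 3 and 4.9% in pattern 1.

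**Simulation check.** A neighbouring pattern (20% at Month 3 vs 20% at Month 12, D = 8) gives bias 0.80 and a significant result favouring the drug 14.0% of the time by formula; simulation gave 0.81 and 14.6%, against 2.45% nominal.

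**The case against.** Four points on the other side have weight.

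**LOCF also shrinks a real effect.** This is the δ·fA term. With a true 3.5-point benefit, pattern 2 straddles zero and pattern 3 is at most +0.39. The no-effect figures alone would overstate the problem. This stands, and both columns are shown for that reason.

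**Fewer and earlier exits need not favour the drug.** A reader might infer that they always do. Pattern 4 shows otherwise: with fewer azeliragon dropouts, they must leave early enough for fA to exceed fP. Under no effect, only equal counts with earlier exits guarantee the direction.

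**Phase 2 does not predict the harmful pattern.** A reader might link it to the larger share of patients worsening by at least 10 points "on the ADAS-cog (relative to Baseline scores) at Months 3 and 6". Protocol 1.1.3 reports that for 20 mg/day and says it was not noted at 5 mg/day. It was cognitive worsening, which LOCF would carry forward against azeliragon. In the same study's 5 mg comparison, LOCF gave p = 0.03 and multiple imputation p = 0.008. That is limited evidence, but it does not suggest that LOCF flattered the drug.

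**Other analyses cover the ground.** The tipping-point, Copy Reference, completer and observed-case analyses are all planned, and SAP section 9 lists withdrawals with study day and reason. This limits the consequence.

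None of these makes the stated condition sufficient for the stated property.

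**Conclusion.** The claim that LOCF is conservative when azeliragon has no more dropouts than placebo is not guaranteed under the plan's own premise of steady worsening. LOCF can favour azeliragon with equal or fewer dropouts if they leave sufficiently earlier. In the two illustrative patterns where it does so under no effect, the bias is 0.33 to 0.82 ADAS-cog points, or about 10% to 24% of the design difference (0.33/3.5 and 0.82/3.5). With a true 3.5-point benefit, the same patterns give −0.13 to +0.39.

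These sizes rest on the assumed decline, linearity, non-selective dropout and chosen exit times. The direction of the argument needs only that earlier leavers forgo more decline.

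The rejection rates of about 6.5% to 15% might be read as the trial's type I error. They are not: LOCF carries no alpha, and success requires p < 0.049 in the primary MMRM for both endpoints in both sub-studies. The defect lies in what a favourable LOCF result may be said to show. It should be corrected, but it does not threaten the primary conclusion.

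**What to change.** In SAP 5.2.1, delete the statement that LOCF is conservative under the dropout-count condition, and the matching justification of the LOCF endpoint analysis. Treat the parallel wording in Protocol 9.5.2 as superseded. Name the Copy Reference and delta tipping-point imputations, already planned in SAP 5.2.1 and 6.2, as the key missing-data sensitivity analyses. Keep LOCF as descriptive or supportive.

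Add one display by arm: time to last on-treatment value of each co-primary endpoint, using visit and withdrawal dates already collected. Replacing the count condition with a timing condition is not advised as a guarantee, since that would in turn depend on linear decline and non-selective dropout.

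The cost is a SAP wording change and one display, with no new data or imputation model. The small downside is that LOCF can no longer be cited as conservative support on head-count alone.
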